11.2. Criteria for Resuming Treatment Held for Adverse Event Related to Avelumab

If a subject's avelumab treatment is held due to an adverse event that is possibly, probably or definitely related to avelumab, the subject may resume treatment with avelumab when the related adverse event resolves to \leq Grade 1 or to patient's baseline value, with the following exceptions:

- Subjects may resume treatment in the presence of Grade 2 fatigue or alopecia of any grade.
- Subjects who have not experienced a Grade 3 drug-related skin AE may resume treatment in the presence of Grade 2 skin toxicity
- Subjects with a Grade 2 AST/ALT or total bilirubin may resume treatment IF patient's respective baseline AST/ALT or total bilirubin was Grade 1 and the reason for patient's dose delay was NOT due to a 2 or more grade increase in AST/ALT or total bilirubin.
- Subjects with combined Grade 2 AST/ALT AND total bilirubin values meeting discontinuation parameters should have treatment permanently discontinued
- Drug-related pulmonary toxicity or colitis must have resolved to baseline before treatment is resumed
- Drug-related endocrinopathies adequately controlled with only physiologic hormone replacement may resume treatment.

The subject's baseline value is defined as the most recent value preceding initiation of the patient's first dose of avelumab.

In the event study treatment is held due to an event the investigator feels is unlikely related or not related to avelumab (e.g. hold study drug per investigator discretion in order to evaluate appropriate attribution to disease versus drug), then resumption of avelumab may proceed according to the medical judgement of the investigator (with maintained accordance to other protocol sections).

If treatment is delayed > 4 weeks (28 days) from the last dose of avelumab, the subject must be permanently discontinued from study therapy, except as may be specified in Sections 9.4, 11.2 and 11.7.

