11.6. Management of Immune-Related Adverse Events (irAEs)

Since inhibition of PD-L1 stimulates the immune system, immune-related adverse events (irAEs) may occur. **Any adverse event judged by the investigator to be possibly, probably or definitely immune-related should be managed according to the guidance in this section for the management of immune-related adverse events, except for circumstances in which local or other standards known to exist are felt by the investigator to present a more medically appropriate course of management.**

Treatment of irAEs is mainly dependent upon severity (NCI-CTCAE grade):

- Grade 1 to 2: treat symptomatically or with moderate dose steroids, more frequent monitoring
- Grade 1 to 2 (persistent): manage similar to high grade AE (Grade 3 to 4)
- Grade 3 to 4: treat with high dose corticosteroids

Some potential irAEs described with anti-PD-L1 drugs such as avelumab may be similar to toxicities related to disease (e.g. diarrhea related to adenocarcinoma of the small intestine). In general: Rule out non-inflammatory causes; if non-inflammatory cause is identified, treat accordingly and continue study treatment according to protocol.

Corticosteroids are a primary therapy for immuno-oncology drug-related adverse events. Patients treated for irAEs with IV steroids may be switched to an equivalent dose of oral corticosteroids (e.g. prednisone) at start of tapering or earlier, once sustained clinical improvement is observed. Lower bioavailability of oral corticosteroids should be taken into account when switching to the equivalent dose of oral corticosteroids.

MANAGEMENT of GASTROINTESTINAL IMMUNE-RELATED ADVERSE EVENTS (irAEs)		
Diarrhea / Colitis	Management	Follow-Up

Grade 1
 
Diarrhea: < 4 stools/day over baseline
 
Colitis: Asymptomatic
	
 • Continue avelumab therapy per protocol. • Symptomatic treatment (e.g. loperamide). 	
 • Close monitoring for worsening symptoms. • Educate patient to immediately report worsening. 
If worsens:
 
 • Treat as Grade 2, or Grade 3 to 4.

MANAGEMENT of GASTROINTESTINAL IMMUNE-RELATED ADVERSE EVENTS (irAEs)		
Diarrhea / Colitis	Management	Follow-Up

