
Grade 2
 
Diarrhea: 4 to 6 stools per day over baseline; IV fluids indicated < 24 hours; not interfering with ADL
 
Colitis: Abdominal pain; blood in stool
	
 • Delay avelumab therapy per protocol. • Symptomatic treatment. 	
If improves to Grade ≤1:
 
 • Resume avelumab therapy per protocol. 
If persists > 5-7 days or recurs:
 
 • treat as Grade 3 or 4.

Grade 3 to 4
 
Diarrhea (Grade 3): ≥ 7 stools per day over baseline; incontinence; IV fluids ≥ 24 hrs; interfering with ADL
 
Colitis (Grade 3): Severe abdominal pain, medical intervention indicated, peritoneal signs
 
Grade 4: Life-threatening, perforation
	
 • Withhold avelumab for Grade 3 • Permanently discontinue avelumab for Grade 4 or recurrent Grade 3 • 1.0 to 2.0 mg/kg/day methylprednisolone IV or equivalent. • Add prophylactic antibiotics for opportunistic infections. • Consider lower endoscopy. 	
If improves:
 
 • Continue steroids until Grade ≤ 1, then taper over at least 1 month; resume avelumab therapy following steroids taper (for initial Grade 3) 
If worsens, persists > 3 to 5 days, or recurs after improvement:
 
 • Add infliximab 5 mg/kg (if no contraindication). Note: Infliximab should not be used in cases of perforation or sepsis.

Opiates/narcotics may mask symptoms of perforation. Infliximab should not be used in cases of perforation or sepsis.

MANAGEMENT of DERMATOLOGIC IMMUNE-RELATED ADVERSE EVENTS (irAEs)		
Rash	Management	Follow-Up

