
Grade 1 to 2 Covering ≤ 30% body surface area (BSA)
	
 Continue avelumab therapy per protocol. Symptomatic therapy (for example, antihistamines, topical steroids) 	
If persists > 1 to 2 weeks or recurs:
 
 withhold avelumab therapy Consider skin biopsy. 
 Consider 0.5 to 1.0 mg/kg/day methylprednisolone IV or oral equivalent. Once improving, taper steroids over at least 1 month, consider prophylactic antibiotics for opportunistic infections, and resume avelumab therapy following steroids taper. 
If worsens:
 
 Treat as Grade 3 to 4.

Grade 3 Covering > 30% BSA;
 
Grade 4 life threatening consequences
	
 Withhold avelumab for Grade 3 Permanently discontinue for Grade 4 or recurrent Grade 3. Consider skin biopsy. Dermatology consult. 1.0 to 2.0 mg/kg/day methylprednisolone IV or IV equivalent. Add prophylactic antibiotics for opportunistic infections. 	
If improves to Grade ≤ 1:
 
 Taper steroids over at least 1 month and add prophylactic antibiotics for opportunistic infections Resume avelumab therapy following steroids taper (for initial Grade 3).

MANAGEMENT of PULMONARY IMMUNE-RELATED ADVERSE EVENTS (irAEs)		
Pneumonitis	Management	Follow-Up

Grade 1 Radiographic changes only
	
 Consider withholding avelumab therapy. Monitor for symptoms every 2 to 3 days. Consider Pulmonary and Infectious Disease consults. 	
 Re-assess at least every 3 weeks. 
If worsens:
 
 Treat as Grade 2 or Grade 3 to 4.

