
Grade 2 Mild to moderate new symptoms
	
 Withhold avelumab therapy Pulmonary and Infectious Disease consults. Monitor symptoms daily, consider hospitalization. 1.0 to 2.0 mg/kg/day methylprednisolone IV or IV equivalent. Add prophylactic antibiotics for opportunistic infections Consider bronchoscopy, lung biopsy. 	
 Re-assess every 1 to 3 days. 
If improves:
 
 When symptoms return to Grade \leq 1, taper steroids over at least 1 month and then resume avelumab therapy per protocol following steroids taper and consider prophylactic antibiotics. 
If not improving after 2 weeks or worsening:
 
 Treat as Grade 3 to 4.

Grade 3 to 4 Grade 3: Severe new symptoms; New / worsening hypoxia; Grade 4: life-threatening
	
 Permanently discontinue avelumab therapy per protocol. Hospitalize. Pulmonary and Infectious Disease consults. 1.0 to 2.0 mg/kg/day methylprednisolone IV or IV equivalent. Add prophylactic antibiotics for opportunistic infections. Consider bronchoscopy, lung biopsy. 	
If improves to Grade \leq 1:
 
 Taper steroids over at least 1 month. 
If not improving after 48 hours or worsening:
 
 Add additional immunosuppression (e.g. infliximab, cyclophosphamide, intravenous immunoglobulin, or mycophenolate mofetil).

Evaluate with imaging and pulmonary consultation as appropriate.

MANAGEMENT of HEPATIC IMMUNE-RELATED ADVERSE EVENTS (irAEs)		
Elevated Liver Function Test (LFT)	Management	Follow-Up

Grade 1
 
AST or ALT > ULN to 3.0 x ULN and/or total bilirubin > ULN to 1.5 x ULN
	
 Continue avelumab therapy per protocol. 	
 Continue liver function monitoring per protocol. 
If worsens:
 
 Treat as Grade 2 or Grade 3 to 4.

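### The Section 11.6 row for initial Grade 3 diarrhea/colitis lets avelumab resume without the return to baseline that Section 11.2 requires for colitis, and the 28-day exception lists in 11.1 and 11.2 do not match

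*Combined protocol and SAP*

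**What the plan says.** **Section 11.2.** Avelumab held for a related event may restart at Grade 1 or lower, or at the patient's baseline, subject to listed exceptions. One exception is stricter than the general rule: "Drug-related pulmonary toxicity or colitis must have resolved to baseline before treatment is resumed". Baseline is the last value before the first dose.

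**Section 11.6, lead-in.** Events judged immune-related "should be managed according to the guidance in this section for the management of immune-related adverse events", unless the investigator considers local or other known standards medically more appropriate. Section 11.2 is not mentioned.

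**Section 11.6, tables.** Three rows for these toxicities lead back to dosing:

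- Initial Grade 3 diarrhea/colitis: steroids until Grade 1 or lower, "then taper over at least 1 month; resume avelumab therapy following steroids taper (for initial Grade 3" only; Grade 4 and recurrent Grade 3 are discontinued.
- Grade 2 diarrhea/colitis: "Delay avelumab therapy per protocol" and, at Grade 1 or lower, "Resume avelumab therapy per protocol".
- Grade 2 pneumonitis: when symptoms reach Grade 1 or lower, "taper steroids over at least 1 month and then resume avelumab therapy per protocol following steroids taper".

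Grade 3 to 4 pneumonitis has no route back: "Permanently discontinue avelumab therapy per protocol".

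**Delay limit.** Sections 11.1 and 11.2 both require permanent discontinuation once the delay exceeds 28 days from the last dose. Section 11.1 excepts Sections 9.4 and 11.3. Section 11.2 excepts 9.4, 11.2 and 11.7. No Section 11.7 exists; Section 14.5.12 uses that number for the immune-related guidance, which is now 11.6.

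**The concern.** The 11.2 exception has one function: to forbid, for bowel and lung toxicity, what the general rule would allow, namely re-dosing at a residual Grade 1 that is above baseline. The initial Grade 3 colitis row does not carry that condition, and it is the table that the lead-in tells sites to use. A patient with a normal baseline and residual Grade 1 colitis after the taper could be re-dosed under 11.6 although 11.2 bars it.

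The delay limit adds a second uncertainty for the same patient. After the taper, 11.6 says to resume, while 11.1 as printed says to discontinue permanently.

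What is at stake is consistent handling of re-exposure after a serious immune-related event, in a trial with the safety profile as a primary objective.

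**Working it through.** **1. The three rows against Section 11.2.** The plan gives no figure to reproduce here, so the check is of the text.

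| 11.6 row | Role of Grade 1 or lower | Baseline condition in row | Says per protocol | Reading against 11.2 |
|---|---|---|---|---|
| Initial Grade 3 diarrhea/colitis | Starts the taper; resumption follows the taper | None | No | Mismatch |
| Grade 2 diarrhea/colitis | Direct trigger for resumption | None | Yes | Ambiguous |
| Grade 2 pneumonitis | Starts the taper; resumption follows the taper | None | Yes | Ambiguous |

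In the Grade 2 colitis row, the hold and the restart are both tied to the protocol, which suggests a reference to 11.1 and 11.2. If that is right, the row imports the baseline rule. The pneumonitis row can be read in the same way. The initial Grade 3 colitis row has no such wording.

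**2. The taper against the 28-day limit.** Section 11.1 counts the delay from the day of the last dose to the day of the next. Let *d* be the day after the last dose on which Grade 1 or lower is reached, and take one month as 28 to 31 days. Earliest re-dose = *d* + 28 to *d* + 31.

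- *d* = 1: day 29 to 32
- *d* = 7: day 35 to 38
- *d* = 14: day 42 to 45

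All exceed 28 days, so every taper-then-resume row needs an exception. Section 11.2 appears to supply one through its stale 11.7. Section 11.1 as printed does not, because present Section 11.3 covers infusion reactions and contains no provision for longer delays. The last row of the 11.6 tables discontinues for Grade 2 or 3 events lasting 12 weeks or longer. That threshold would do little if 28 days always ended treatment, so the taper-then-resume rows appear to be meant to operate.

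**3. How many patients.** Section 4.5 reports treatment-related colitis of Grade 3 or higher in 2 of 717 expansion-cohort patients. It itemizes the Grade 4 patients (7 + 5 + 1 + 1 = 14) and the Grade 5 patients (2 + 2 = 4), and colitis is in neither list. Both cases were therefore Grade 3.

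- Rate: 2/717 = 0.28%, exact 95% CI 0.03% to 1.0%.
- Expected in 25 patients: 25 × 0.00279 = 0.07 (0.01 to 0.25).
- Chance of at least one: 1 − (1 − 0.00279)^25 = 6.7% (0.8% to 22%).

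Only patients who settle at Grade 1 above baseline are affected, so these figures are upper values for the Grade 3 row.

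The documents give no rate for Grade 2 colitis or Grade 2 pneumonitis. Neither event is in the Section 4.5 list of any-grade events at 2% or more. Assuming that list is complete, each is at most 14/717 = 1.95%, so between 0 and 25 × 0.0195 = 0.49 patients are expected for each. The list is not stated to be exhaustive, so this is a weak bound.

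**The case against.** The strongest reply is that the rules do not strictly contradict each other. In the initial Grade 3 colitis and Grade 2 pneumonitis rows, Grade 1 or lower starts the taper, and neither row states the grade required on the day of re-dosing. The mandatory wording in 11.2 can apply at that point. The only row with a direct Grade 1 trigger defers to the protocol. This stands as a limit: waiting for baseline satisfies everything. It does not remove the point for initial Grade 3 colitis, because that row tells the site to resume after the taper, gives no pointer to 11.2, and is the place to which the lead-in sends the site.

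A reader might infer that all three rows contradict 11.2. The documents do not support that, because two of them say per protocol.

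The gastrointestinal rows also cover diarrhea, which the 11.2 exception does not name. For diarrhea without colitis, Grade 1 or lower agrees with the general rule in 11.2. This is correct, and the fix has to preserve it.

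On the delay limit, a reader might infer that 11.1 was meant to bar re-dosing after any taper. The numbering is stale, however. If 11.7 means the present 11.6, the same one-step shift makes 11.3 in Section 11.1 the present 11.2, and the immune-related exception would then reach both sections. That is plausible but is inference. As printed, the lists differ. This is a separate numbering defect and does not make the baseline mismatch more serious.

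Finally, the difference may rarely be visible. Grade 1 colitis is defined as asymptomatic and no endoscopy is scheduled. Grade 1 pneumonitis is defined as "Radiographic changes only" and could show on the scheduled chest imaging, but its row is one of the two ambiguous ones.

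**Conclusion.** The point holds in a narrow form and is minor. One row, initial Grade 3 diarrhea/colitis, permits resumption without the baseline condition that 11.2 makes mandatory for colitis, and nothing states which section governs. The Grade 2 colitis and Grade 2 pneumonitis rows are unclear rather than inconsistent. The 28-day exception lists in 11.1 and 11.2 differ as printed, and every one-month taper depends on them.

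The expected number of Grade 3 colitis cases is about 0.07 in 25 patients, and fewer would settle at Grade 1 above baseline. This assumes that the expansion-cohort rate, which comes from other tumor types, carries over to small intestinal adenocarcinoma. It also assumes a baseline of Grade 0, which is likely because exclusion criterion 23 lets the investigator exclude patients with immune colitis or inflammatory bowel disease.

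A reader might infer some effect on the efficacy analysis. There is none on the definition of objective response, the sample size of 25 or the error rates.

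**What to change.** In one amendment:

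1. In the 11.6 initial Grade 3 diarrhea/colitis row, add: *and only once colitis has resolved to baseline (Section 11.2)*.
2. Add the same pointer to the Grade 2 colitis row and, worded for pulmonary toxicity, to the Grade 2 pneumonitis row. Keep Grade 1 or lower as the threshold for diarrhea without colitis.
3. Correct 11.7 to 11.6 in Sections 11.2 and 14.5.12.
4. List 11.6 as an exception to the 28-day limit in both 11.1 and 11.2. This agrees with the taper-then-resume rows, including those for rash, renal and other immune-related events, and with the 12-week discontinuation limit.

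The 11.6 resumption rules for other toxicities, including the endocrine and hypophysitis rows, stay as they are.

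The cost is a wording amendment with no added assessments. The downside is that a few patients with residual Grade 1 colitis or pneumonitis stay off drug longer, which 11.2 already requires.

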11.3. Guidelines for the Management of Infusion Reaction

Since avelumab is administered via intravenous (IV) infusion, an infusion-related reaction may occur with symptoms possibly including but not limited to fever, chills, rigors, diaphoresis, and headache. In the event of an actual or suspected infusion reaction, avelumab treatment should be modified according to the guidelines listed below in conjunction with any overriding local policies and procedures for the management of infusion-related reactions.

If avelumab infusion rate has been decreased by 50% or interrupted due to an infusion reaction, it must remain decreased for the next scheduled infusion. If no infusion reaction is observed in the next scheduled infusion, the infusion rate may be returned to baseline at the subsequent infusions based on investigator's medical judgement. The total infusion time for avelumab should not exceed 120 minutes. If a subject experiences a Grade 3 or 4 infusion-related reaction at any time, the subject must discontinue study drug.

Infusion Modifications for Symptoms of Infusion Reaction	
NCI CTCAE Severity Grade	Avelumab Treatment Modification

Grade 1 - Mild
 
 • Mild transient reaction; • infusion interruption not indicated • intervention not indicated. 	
 • Decrease the avelumab infusion rate by 50% and monitor closely for any worsening.

Grade 2 - Moderate
 
 • Therapy or infusion interruption indicated, but responds promptly to symptomatic treatment (e.g. antihistamines, NSAIDs, narcotics, IV fluids); • Prophylactic medications indicated for ≤ 24 hours. 	
 • Temporarily discontinue avelumab infusion • Resume infusion at 50% of previous rate as soon as infusion-related reaction has resolved or decreased to at least Grade 1 in severity 
Monitor closely for any recurrence or worsening.

Grade 3 or Grade 4 - Severe or Life-threatening	

Grade 3:
 
 • Prolonged (e.g. not rapidly responsive to symptomatic medication and/or brief interruption of infusion); • Recurrence of symptoms following initial improvement; • Hospitalization indicated for clinical sequelae. 
Grade 4:
 
 • Life-threatening consequences; 
Urgent intervention indicated.
	
 • Stop the avelumab infusion immediately • Disconnect bag infusion tubing from the patient. 
Permanently discontinue avelumab treatment.

IV = intravenous, NCI CTCAE = National Cancer Institute Common Terminology Criteria for Adverse Events,

NSAIDs = Non-steroidal anti-inflammatory drugs.

Additional Modifications for Patients with Grade 2 Infusion-Related Reactions:

In the event a Grade 2 infusion-related reaction does not improve or worsens after implementation of the modifications indicated in the above table (including reducing the infusion rate by 50%), the investigator may consider treatment with corticosteroids, and the infusion should not be resumed for that cycle. At the next cycle, the investigator may consider the addition of H2-blocker antihistamines (e.g. famotidine or ranitidine), meperidine, or ibuprofen in supplement to the premedications recommended in Section 9.1. Prophylactic steroids are NOT permitted.

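### Section 11.3's extra Grade 2 paragraph conflicts with its own table and stop rule when symptoms return after a half-rate restart, or when a reaction fails to respond to interruption or medication

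*Combined protocol and SAP*

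**What the plan says.** Section 11.3 handles infusion reactions in three places.

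- **Lead text.** "If a subject experiences a Grade 3 or 4 infusion-related reaction at any time, the subject must discontinue study drug". The lead text also says that a rate that was halved, or an infusion that was interrupted, stays at the reduced rate for the next scheduled infusion, so it expects some patients to be dosed again after a reaction.
- **Table, Grade 2 row.** The infusion is stopped temporarily, then: "Resume infusion at 50% of previous rate as soon as infusion-related reaction has resolved or decreased to at least Grade 1 in severity". The row closes with "Monitor closely for any recurrence or worsening" and gives no action if that happens.
- **Table, Grade 3 or 4 row.** The Grade 3 criteria include "Recurrence of symptoms following initial improvement" and a prolonged reaction, for example one "not rapidly responsive to symptomatic medication and/or brief interruption of infusion". The action is "Permanently discontinue avelumab treatment".
- **Additional Modifications paragraph, below the table.** It is headed as applying to Grade 2 reactions. Its trigger is "In the event a Grade 2 infusion-related reaction does not improve or worsens after implementation of the modifications indicated in the above table", with the bracketed addition "including reducing the infusion rate by 50" per cent. The investigator may consider corticosteroids, the infusion is not resumed in that cycle, and H2-blockers, meperidine or ibuprofen may be added to the premedication at the next cycle.

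**The concern.** The same clinical event can be given two grades with opposite dosing consequences. Under the table and the lead text the patient stops avelumab for good. Under the paragraph the patient misses the rest of one infusion and is then considered for the next dose with more premedication. The paragraph is the more specific text for a reaction that goes badly after the first measures, so it is the text that staff in the infusion room may well follow.

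What is at stake is re-exposure of a patient whom the protocol says must stop. There is a smaller effect on the data. Safety is a primary objective (Section 3.1) and adverse events are to be summarised by severity (Section 17.3), so the same event could be recorded as Grade 2 for one patient and Grade 3 for another. Section 9.7 also bars later re-treatment of patients who meet the safety withdrawal criteria, so unclear grading could carry into that decision.

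**Working it through.** The conflict is a comparison of texts. I followed one patient through the section and then sorted the events that the paragraph could cover.

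**One patient.**
1. A Grade 2 reaction occurs and the infusion is stopped.
2. Restart at half rate is allowed only once the reaction has resolved or fallen to Grade 1. A patient who restarts has therefore already improved.
3. The symptoms come back at half rate.
4. By the table this is return of symptoms after improvement: Grade 3, permanent discontinuation. The lead text makes that mandatory.
5. If the event is instead described as a Grade 2 reaction that has got worse after the table's measures, the paragraph applies: no more drug this cycle, premedication considered for the next.

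**Events the paragraph could cover.**

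| Event | Table and lead text | Paragraph | Conflict? |
|---|---|---|---|
| (a) Symptoms return after improvement and half-rate restart, handled as worsening | Grade 3, stop permanently | Grade 2, next dose implied | Yes |
| (b) No improvement, in the sense of no rapid response to interruption or symptomatic medication | Grade 3 (prolonged), stop permanently | Grade 2, next dose implied | Yes |
| Residual Grade 1 symptoms that persist at half rate | Not clearly Grade 3 | Applies | No |
| Residual symptoms that intensify without meeting a Grade 3 criterion | Not Grade 3 | Applies | No |
| Grade 1 reaction slowed by 50% that becomes Grade 2 for the first time | Grade 2 | Applies | No |

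**Does another section settle it?** Section 11.1 and the lead text of 11.3 defer to local practice or policy, which does not say which of the two protocol instructions is right. Section 9.4 refers discontinuation for adverse events back to Section 11.

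**Scale only.** The documents give no rate for events (a) or (b). Section 4.5 reports, for 717 pooled patients, treatment-related infusion reactions in 18.7% at any grade and in 7 patients at Grade 3 or higher. Assuming those rates held in this trial:
- Any grade: 25 × 0.187 = 4.7 expected. The disputed events are a subset, so this is a ceiling on their expected number.
- Grade 3 or higher: 7/717 = 0.976%, and 25 × 0.00976 = 0.24 expected. The exact 95% interval for 7/717 is 0.39% to 2.00%, which gives 0.10 to 0.50 expected.
- Chance of at least one Grade 3 or higher: 1 − (1 − 0.00976)^25 = 21.8%.

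None of these figures measures the disputed events. They come from other tumour types, and the documents do not say how a returning reaction was graded there.

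**The case against.** The strongest reply is that the protocol already has a controlling rule. The lead text says that a Grade 3 or 4 reaction at any time means stopping, while the paragraph is limited by its heading to Grade 2 and is permissive about treatment. Once a reaction meets a Grade 3 criterion it leaves the paragraph's scope, and grade tables are ordinarily applied to the current grade. This largely stands, and it is the better reading. What it does not remove is that the paragraph, taken at its word, describes events that can already be Grade 3, still calls them Grade 2 and gives no instruction to re-grade.

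A second reply is that the paragraph speaks of worsening, not recurrence, and that the Grade 2 row names the two separately. This also stands in part. A reader might infer that any worsening after a half-rate restart must be Grade 3. The documents do not support that: restart is allowed with residual Grade 1 symptoms, and if these intensify, the table does not make that a recurrence. Nor is the paragraph left without a purpose, since the last three rows of the table in the working remain for it.

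A reader might also infer that the paragraph orders another dose. It does not. It only allows premedication to be considered at the next cycle, which implies a dose without requiring one.

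**Conclusion.** The conflict is real but confined to situations (a) and (b), and it depends on how the event is described at the bedside. In (a) it arises if returning symptoms are handled as a Grade 2 reaction that has worsened. In (b) it arises if lack of improvement means failure to respond rapidly to interruption or symptomatic medication. The mandatory stop sentence is best taken as governing both, so the protocol is not wholly silent on which instruction prevails, although a reader could suppose so. The defect is that the paragraph can lead an investigator away from that sentence.

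The number of patients affected is unknown, probably very small and possibly zero. Confidence is moderate, because the grading of worsening residual symptoms is a clinical judgement that the table leaves open. Nothing here bears on the sample size, the power or the rule of 4 responses among 25. The change should be made because the consequence is possible re-exposure and the remedy is cheap.

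**What to change.** Add three statements to the Additional Modifications paragraph:

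1. A reaction that fails to improve or gets worse after the table's measures must be re-graded against the table.
2. If any Grade 3 criterion is then met, including return of symptoms after improvement and restart, or no rapid response to interruption or symptomatic medication, avelumab is permanently discontinued.
3. Added premedication at the next cycle applies only to reactions that remain within the Grade 1 or Grade 2 definitions.

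Acute corticosteroids can stay as an option in every case. A cross-reference to the Grade 3 row at the end of the Grade 2 row would supply the action now missing there.

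The cost is wording in one section, with no added procedures or patients. The downside is that an occasional patient who might have been rechallenged would stop the drug, which is what the lead text already requires.
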